General:																				
[REDACTED]																				
[REDACTED]																				
[REDACTED]																				
[REDACTED]																				
[REDACTED]																				
[REDACTED]																				
[REDACTED]																				
[REDACTED]																				
[REDACTED]																				
[REDACTED]																				
[REDACTED]																				
[REDACTED]																				
[REDACTED]																				
[REDACTED]																				
[REDACTED]																				
[REDACTED]																				
[REDACTED]																				
[REDACTED]																				
[REDACTED]																				

Study Day (±window)	Screen	Study Treatment																	
		1	3-5	6-8	9-11	14 ± 2	17-18	21 ± 2	24-25	28 ± 2	35 ± 2	42 ^b ± 3	49 ± 3	56 ± 3	70 ± 3	84 ^b ± 6	EOT ^{b,c} ± 3	Follow-up (4 wks after EOT ± 7d)	
Study Visit	V1	V2	V4	V6	V7	V8	V9	V10	V11	V12	V12a	V13	V13a	V14	V15	V16	V17	V18	
[REDACTED]	■																		
[REDACTED]	■	■			■	■	■		■		■		■			■	■	■	
[REDACTED]	■				■	■	■		■		■			■	■	■	■	■	
[REDACTED]	■								■										
[REDACTED]	■																		
[REDACTED]	■																		
[REDACTED]	■																		
[REDACTED]	■																		
[REDACTED]	■																		
[REDACTED]	■																		
[REDACTED]	■																		
[REDACTED]	■																		
[REDACTED]	■																		
[REDACTED]	■																		
[REDACTED]	■																		
[REDACTED]	■																		
[REDACTED]	■																		
[REDACTED]	■																		
[REDACTED]	■																		
[REDACTED]	■																		
[REDACTED]	■																		
[REDACTED]	■																		
[REDACTED]	■																		
[REDACTED]	■																		
[REDACTED]	■																		
[REDACTED]	■																		

[figure not shown]
a. Screening assessments are to be completed within the 7 days prior to start of treatment unless otherwise specified.
 b. To be completed even if treatment was completed prior to these visits due to a successful outcome. Main study phase EOT, Day 42 and Day 84 assessments are required for all patients. FU assessments are required for all patients who do not continue therapy beyond Day 90. Patients with a successful overall outcome are required to return for all

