- four visits. Patients withdrawn from study drug or with an unsuccessful overall outcome are required to return for the main study phase EOT visit and FU visit but will not be asked to return for the Day 42 and Day 84 visits; however, survival status will be obtained at these timepoints.
- c. If the main study phase EOT occurs within 1 week of a scheduled visit, the assessments completed at that visit do not need to be repeated; however, the Investigator must ensure that all assessments required for main study phase EOT have been completed. As an example, Day 84 and main study phase EOT would be the same for a patient who completes 12 weeks of therapy and stops drug. For patients who will receive ET beyond Day 90, the Day 84 visit and the main study phase EOT visit will be combined into a single Day 84/EOS/EOT visit on approximately Day 90. Subsequent visits will be every 4 weeks to assess the safety of continued treatment and to assess the need for further treatment, and there will be a FU visit 4 weeks after ET is completed.
 - d. Only for women of childbearing potential. At screening and on the visits indicated in the schedule of event, only if patient is not hospitalized.
 - e. During 6 months prior to treatment start. If the qualifying infection was diagnosed before baseline, data regarding the prior symptoms and prior evaluation(s) of the invasive fungal infection should be noted here.
 - f. All major illnesses or medical history should be captured with particular attention to the 3 months prior to treatment start.
 - g. Enrolment may occur up to and including Day 1, prior to first dosing
 - h. Prior and concomitant medication to be reported during 4 weeks prior to treatment start and up to the 4-week FU visit; for chemotherapy a summary of regimens during 12 weeks prior to treatment start should be provided. For T-cell immunosuppressive medications (e.g. cyclosporine, tacrolimus, monoclonal antibodies or nucleoside analogues) given within 90 days prior to screening or any dosing prior to study entry that support the host factor criteria "Treatment with other recognized T-cell immunosuppressants" at the time of the initial diagnosis of the fungal infection.. All other medications given within 4 weeks prior to screening or any dosing prior to study entry that support the host factor criteria "Prolonged use of Corticosteroids". All medications taken during the treatment period. All medications taken during the 4-week post-treatment period.

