For all patients except those receiving ET, the Follow-up Visit will take place 4 weeks (± 7 days) after the last administration of study drug, and may occur before or after Day 42 and/or Day 84 (i.e., it is not necessarily the "end of study" visit for a given patient). For those patients receiving extended F901318 treatment, the main study phase EOS and EOT will be the same visit and will

occur at approximately Day 90, and, the follow-up safety visit will take place 4 weeks (± 7 days) after the last administration of study drug.

Patients with a successful overall outcome at the main study phase EOT, who subsequently require further treatment with F901318 before the 28-day post-treatment Follow-up Visit, may receive further treatment with F901318 following consultation with the MM. In this situation, stopping treatment with F901318 then resuming treatment will be considered to be a treatment interruption, and if the interval is more than 48 hours redosing should begin with a loading dose regimen. In addition, appropriate diagnostic tests should be undertaken to determine the cause of the change in clinical status and the susceptibility to F901318 of any identified IFD.

Patients with a successful overall outcome at the main study phase EOT prior to Day 42 must return for Day 42 and Day 84 Visits, even if they are no longer under study treatment. If the administration of systemic antifungals as prophylaxis is anticipated, patients should stay on study treatment through Day 42.

Patients with an unsuccessful overall outcome at the main study phase EOT and requiring alternative systemic antifungal therapy will not be asked to return for Day 42 and/or Day 84 Visits; however the survival status at these timepoints will be collected at a minimum.

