6.3.1.1 Clinical Response

Clinical response will be based on clinical signs, physical findings, and symptoms relevant to each patient. The Investigator will be responsible for identifying and assessing clinical signs, physical findings, and symptoms related to the IFD reported for each patient. Assessment of clinical response will be based on changes from baseline signs, findings, and symptoms. Clinical signs, physical findings, and symptoms will be assessed [REDACTED]

[REDACTED] as shown in Table 1. Assessment at Day 42 and at Day 84 is required for all patients, including those who completed treatment before these visits.

For patients who receive ET with F901318, the Investigator's assessment of clinical response will be recorded at each visit to support continued treatment.

Baseline symptoms may need to include symptoms present at the time of the initial diagnosis of the qualifying infection. This situation may arise when a patient has had a prior therapy, responded to that therapy, but then developed intolerance to the therapy and is hence started on F901318 therapy without active symptoms at the point of study enrolment. Such prior symptoms will be recorded in the appropriate section of the eCRF.

The results of assessments of clinical signs, physical findings, and symptoms (including those performed outside of these mandatory scheduled timepoints) will be recorded in the eCRF.

An assessment of the patient's clinical response (all non-radiological clinical signs, physical findings, and symptoms related to IFD) will be recorded [REDACTED]

(Note that for patients planning to receive ET beyond Day 90, the Day 84 visit and the main study phase EOT visit will be combined into a single Day 84/EOS/EOT visit on approximately Day 90.)

- **Resolution-Complete:**

For patients with attributable clinical symptoms and physical findings of IFD present at baseline, Resolution-Complete is assigned if

- a) there is resolution of all attributable clinical symptoms and physical findings of IFD present at baseline or that appeared at a subsequent prior visit

AND

- b) no new clinical symptoms and physical findings of IFD are noted at the current visit.

For patients lacking attributable clinical symptoms and physical findings of IFD present at baseline*, Resolution-Complete is assigned if

- a) there is resolution of all attributable clinical symptoms and physical findings that appeared at a subsequent prior post-baseline visit

AND

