8.2.2 Primary Efficacy Endpoint

The primary efficacy endpoint is the **DRC-adjudicated overall response** at Day 42 as determined by an independent DRC using a combination of clinical, mycological and radiological results and will be presented overall and by each of the five DRC-adjudicated disease categories as:

- **Success**
- **Failure (where failure includes those patients for whom data at Day 42 cannot be collected or who are considered not evaluable at Day 42)**

The criteria for assessment and categorisation of the DRC-adjudicated overall response will be detailed in the DRC Charter and subsequently specified in the detailed SAP.

Patients withdrawn from study drug due to an unsuccessful overall outcome are required per protocol to return for the main study phase EOT visit but will not be asked to return for the Day 42 and/or Day 84 visits; however, these patients will be considered as failures at all subsequent timepoints.

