*For these categories, the only required data are the clinical and mycological data. The absence of radiological evaluations at a given time point does not prevent assignment to Success-Complete or Success-Partial. The rules defining success are tested in sequence with Success-Complete assigned if its rules are met and Success-Partial otherwise assigned. The rules for Failure are tested next and Failure is assigned if any of its rules are met. The rules for Stable are tested last.

Number and % of patients will be summarised for the 4 categories shown in Table A. N and % will also be summarised for the 3 categories of Success (Success-Complete, Success-Partial), Stable disease (Failure-Stable) and Failure (Failure-Progression, Death, and those patients for whom data at Day 42 cannot be collected or who are considered not evaluable at Day 42).

For statistical primary analysis of overall response rate, values will be assigned to the DRC-adjudicated overall response as follows:

- Success (Success-Complete, Success-Partial),
- Failure (Failure-Stable, Failure-Progression, Death, and those patients for whom data at Day 42 cannot be collected or who are considered not evaluable at Day 42). Patients withdrawn from study medication due to an unsuccessful overall outcome are required per protocol to return for the main study phase EOT visit but will not be asked to return for the Day 42 and/or Day 84 visits; these patients will be considered as failures at all subsequent timepoints.

As a key important analysis, patients with a stable disease outcome will be considered a success, i.e. assigning the DRC adjudicated response to categories as follows.

- Success (Success-Complete, Success-Partial, Failure-Stable)
- Failure (Failure-Progression, Death, and those patients for whom data at Day 42 cannot be collected or who are considered not evaluable at Day 42)

This alternative classification, where stable disease outcome can be considered a successful response in the timeframe of this evaluation, is an important analysis due to the nature of this challenging patient population for whom other therapies have already failed.

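### Protocol Table 1 footnote b contradicts itself and other sections on who attends Day 42 and Day 84, so a responder who stops for a non-efficacy reason can be scored a primary-endpoint failure through missing data alone

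*Protocol*

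**What the plan says.** Footnote b to Protocol Table 1 (Section 4.1) gives three instructions:

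- For everyone: "Main study phase EOT, Day 42 and Day 84 assessments are required for all patients".
- For successes: "Patients with a successful overall outcome are required to return for all" four of the visits named there.
- For those who stop: "Patients withdrawn from study drug or with an unsuccessful overall outcome are required to return for the main study phase EOT visit" and the follow-up visit. They are not called back for Day 42 or Day 84, and only survival status is collected then.

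Other places define the exemption differently:

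- **Figure 1 note (Section 4.1; repeated under Figure A in SAP 3.1):** splits patients by outcome. Successes are assessed, and for failures survival status is obtained.
- **Sections 5.1 and 6.3:** "Patients with an unsuccessful overall outcome at the main study phase EOT and requiring alternative systemic antifungal therapy will not be asked to return"; the visits meant are Day 42 and Day 84. Successes are treated the opposite way: "Patients with a successful overall outcome at the main study phase EOT prior to Day 42 must return for Day 42 and Day 84 Visits".
- **Section 6.3.1.1:** "Assessment at Day 42 and at Day 84 is required for all patients, including those who completed treatment before these visits".
- **Section 8.2.2:** "Patients withdrawn from study drug due to an unsuccessful overall outcome are required per protocol to return for the main study phase EOT visit", but not for Day 42 and/or Day 84. SAP 16.1.1 says the same: "Patients withdrawn from study medication due to an unsuccessful overall outcome are required per protocol to return for the main study phase EOT visit". Both count these patients as failures from then on.
- **Section 4.3.4:** an intolerable adverse event, a clinically significant laboratory value, poor compliance and other non-efficacy reasons lead to withdrawal from drug and from the study, with end-of-treatment (EOT) procedures.

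A missing or non-evaluable Day 42 response is a failure (Protocol 8.2.2 and 8.8.1, SAP 16.1.1 and 16.1.2). All mITT patients stay in the denominator.

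**The concern.** Take a patient who is responding and stops before Day 42 because of an adverse event. Footnote b tells the site both to bring this patient back for all four visits and not to ask for Day 42 or Day 84. Section 4.3.4 points to the second instruction; Sections 5.1, 6.3 and 6.3.1.1 point to the first. If the site follows the second, there may be no Day 42 data and the patient is scored a failure.

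The primary estimate is the Day 42 response rate in the mITT set. It is to be set against external control rates, and the analysis of the first 100 patients is meant to inform whether approval might be sought (Protocol 8.1). Part of that rate would then reflect visit scheduling rather than treatment effect, in an amount that varies by site.

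The visible SAP would not isolate the effect. The per-protocol repeat keeps only patients who complete the main study phase (SAP 5.5), and the modified-response analysis only relaxes the radiology threshold (SAP 16.1.4). The three-category summary in SAP 16.1.1 pools missing responses with progression and death. Estimands are marked not applicable (SAP 2.5), so no strategy for non-efficacy discontinuation is stated.

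**Working it through.** There is no stated power or rate to reproduce: Protocol 8.1 says no formal sample size justification is possible. The check has three parts.

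**1. The rules side by side, for a patient who stops before Day 42**

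| Source | Stops for a non-efficacy reason, responding | Stops with an unsuccessful outcome |
|---|---|---|
| Table 1 footnote b | both asked and not asked | not asked (but the opening rule says all) |
| Figure 1 note | assessed | survival status only |
| 5.1 and 6.3 | must return | not asked if alternative systemic antifungal therapy is also needed |
| 6.3.1.1 | assessed | assessed |
| 8.2.2 and SAP 16.1.1 | not exempted | not asked if withdrawn because of that outcome |
| 4.3.4 | leaves the study after EOT procedures; follow-up visit wherever possible | same |

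**2. When could another required visit supply Day 42 data?** Inputs: the Day 42 window is days 39–45 (SAP 6.5); follow-up is EOT + 28 ± 7 days and EOT is ± 3 days (Protocol 6.1.1); footnote c lets an EOT within one week of a scheduled visit share its assessments. Let X be the stop day, taken as the EOT day.

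- Follow-up can fall in the window if X + 35 ≥ 39 and X + 21 ≤ 45, so X = 4 to 24. At exactly 28 days, X = 11 to 17.
- EOT can fall in the window if X + 3 ≥ 39, so X ≥ 36.
- Footnote c applies if 42 − X ≤ 7, so X ≥ 35.
- Neither visit can serve for X = 1–3 or X = 25–34.

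For those last stop days, not requesting the Day 42 visit means no assessment in the window. For the other days it depends on visit timing and on whether such data may be used. SAP 6.4 presents data by nominal visit, and the DRC charter is not among the documents.

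**3. Size.** If the responders lost this way are a fraction m of the mITT set, the response rate falls by exactly m. Take m = (fraction stopping before Day 42 for a non-efficacy reason) × (fraction of those responding). Neither fraction is in the documents. Assumed range:

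- Low: 0.04 × 0.20 = 0.008, or 0.8 points.
- High: 0.12 × 0.60 = 0.072, or 7.2 points.

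Effect on the exact interval (lower limit: 0.025 quantile of Beta(x, n − x + 1); upper limit: 0.975 quantile of Beta(x + 1, n − x)), for an assumed true rate of 45%:

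| Loss | n = 100 | n = 200 |
|---|---|---|
| 0 points | 45% (35.0–55.3) | 45% (38.0–52.2) |
| 2 points | 43% (33.1–53.3) | 43% (36.0–50.2) |
| 5 points | 40% (30.3–50.3) | 40% (33.2–47.1) |

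**The case against.** The strongest reply is that most of the text already sends responders back. The Figure 1 note, Sections 5.1, 6.3 and 6.3.1.1, and two of the three instructions in footnote b all do so. It would therefore go too far to infer that Table 1 exempts every patient withdrawn from drug. For a responder the footnote contradicts itself, and a site could follow either half.

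Nor do all other sections limit the exemption to failures. Section 4.3.4 takes non-efficacy withdrawals off the study. Sections 5.1 and 6.3 add a condition about alternative therapy that Section 8.2.2 and SAP 16.1.1 lack. Rewording footnote b alone would leave those differences in place.

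A reader might also infer that every such responder becomes a failure. That does not follow. Withdrawn patients are still due a follow-up visit, which the DRC assesses (Protocol 6.3.3), and it or the EOT visit may fall in days 39–45. A patient who needs alternative systemic antifungal treatment is already Failure-progression under Protocol Table 5, so that is not a missing-data failure.

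Scoring missing as failure is prespecified and can only lower the rate, which is conservative in a single-arm study. That stands, but it does not make the rate easier to interpret against external controls when it varies with the instruction a site followed. SAP 7.2 allows a missing category where relevant, which might show some of these cases. SAP 16.1.1 does not commit to separating them for the primary endpoint.

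**Conclusion.** The inconsistency is real and bears on the primary endpoint. A patient can be scored a Day 42 failure through missing data alone if all of these hold: responding, stopped before Day 42 for a non-efficacy reason, needing no alternative systemic antifungal, and without a usable assessment in days 39–45. Stops on days 1–3 or 25–34 are the clearest cases.

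The direction is towards a lower response rate. The size cannot be derived from the documents. Under the assumed 4–12% stopping and 20–60% responding it is at most about 1 to 7 points. It is a ceiling because it supposes that all these patients miss Day 42, that none has usable EOT or follow-up data, that none needs another antifungal, and that all would still be successes at Day 42. Quoting one figure, such as the 3.2 points given by the midpoints (0.08 × 0.40), would imply a precision that the documents do not support.

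**What to change.** **Protocol.** Reconcile footnote b, Section 4.3.4, Sections 5.1 and 6.3, and Section 8.2.2 to one attendance rule based on outcome. Patients who stop study drug without an unsuccessful overall outcome should be asked to attend the Day 42 and Day 84 efficacy assessments if they consent. Section 4.3.4 should make clear that leaving study drug does not by itself end these assessments. Settle whether the need for alternative systemic antifungal therapy is part of the exemption, since the sections now differ. None of this touches when study drug is stopped.

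**SAP.** Bring 16.1.1 into line with that rule. State whether an EOT or follow-up assessment in days 39–45 may serve as Day 42. Report the number of Day 42 failures that are due only to missing data.

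**Cost.** Wording changes, and a few visits after treatment stops that are already in the schedule. If enrolment is too far advanced for the protocol change to help, the SAP count can still be produced.

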4.1.1 Extended Treatment

For patients receiving ET with F901318, visits should be arranged at least once every 4 weeks after the main study phase concludes in the window Day 84-90. Treatment in the ET phase should start on the day following the last treatment day on the main study phase. At each visit, the Investigator should assess the IFD status of the patient. Treatment may be continued if, in the Investigator's opinion, the patient would continue to benefit from further treatment with F901318. At each visit after starting ET, the Investigator must complete the following assessments as described in the Schedule of Events (Table 3) and record the results of the assessments in the eCRF:

- Investigator's assessment of IFD response (as clinically indicated and in accordance with the diagnostic procedures used to identify the IFD)
- Clinical signs and symptoms
- Radiology and/or mycology as clinically indicated and in accordance with local practice
- AE, SAE, AESI, and death (to be documented and reported in accordance with Section 6.4.1)
- Pregnancy and pregnancy test (as appropriate; to be documented and reported in accordance with Section 6.4.1.4)
- Laboratory tests for clinical chemistry and haematology in accordance with Table 7. Increased liver enzymes and bilirubin are to be managed in accordance with Appendix 3. The local laboratory is to be used and analysis at a central laboratory is not required.
- Trough PK sample; regional hub analysis
- Concomitant medication
- Antifungal medication
- Drug accountability
- ECG only if clinically indicated

• [REDACTED]

After each visit, the Investigator must inform the MM of the patient status, the decision taken to continue treatment or not, and the reasons for the decision.

Table 3 Schedule of Events: Extended Treatment (Assessments and Procedures)

Period	Start of Extended Treatment	Extended Treatment	End of Extended Treatment	Follow-up
Study Day (±window)	Main Study Phase Day 85-91 ^a	Every 4 weeks ± 7 days		4 weeks after End of Extended Treatment ± 7 days
[REDACTED]	█			
[REDACTED]	█			
[REDACTED]	█	█	█	█
[REDACTED]	█	█	█	█
[REDACTED]	█		█	
[REDACTED]	█	█	█	
[REDACTED]	█		█	
[REDACTED]	█	█	█	█
[REDACTED]	█	█	█	█
[REDACTED]	█	█	█	█
[REDACTED]	█	█	█	█
[REDACTED]	█		█	
[REDACTED]	█	█	█	█
[REDACTED]	█		█	
[REDACTED]	█	█	█	█
[REDACTED]	█	█	█	█
[REDACTED]	█		█	
[REDACTED]	█	█	█	█
[REDACTED]	█	█	█	█
[REDACTED]	█		█	

- a) The start of ET visit can be the same as the main study phase EOT/EOS visit at Day 84-90, but no later than Day 91. The first day of ET phase dosing will be the day after the last day of dosing in the main study phase.
- b) Only for women of childbearing potential, and only if patient is not hospitalized.
- c) Reason for hospitalization, date of admission and discharge and type(s) of ward, must be recorded in the eCRF.
- d) Diagnostic assessments include mycological culture, histology/cytology, GM, PCR and radiology tests used to confirm enrolment of the patient. It is essential that the same methods are used for both diagnosis and assessment of overall response.
- e) As clinically indicated.
- f) Serum GM must be assessed for all patients with proven or probable IA. Serum GM assessments meeting the protocol defined requirements within 10 days prior to first dose of study drug are acceptable for enrolment requirements.

- g) If used as part of the enrolment criteria, radiology studies should be repeated at these time points. Radiological assessment should be performed in accordance with local practice and as clinically indicated. Radiological examination of the site of IFD should utilize the same x-ray/CT/HRCT/or MRI modality as the baseline radiologic examination.
- h) Bronchoscopic assessment should be performed in accordance with local practice and as clinically indicated.
- i) Neutropenia is defined as $ANC < 0.5 \times 10^9/L$ [$< 500/mm^3$].
- j) Additional samples at unscheduled visits should also be taken if ALT/AST or bilirubin elevations occur (see Appendix 3).
- k) Only in patients with abnormalities observed at ET-EOT
- l) Only if associated with an AE.
- m) [REDACTED]
- n) Trough F901318 samples should be taken within 15 minutes prior to observed dose, but no earlier than 1 hour prior. Abbreviations: AE = adverse event; ANC = absolute neutrophil count; ECG = electrocardiogram; EOS = end of study; EOT = end of treatment; ET = extended treatment; GM = galactomannan; PCR = polymerase chain reaction.

